#### **Standard diet (control group)**

The standard diet will include energy intake of 30-35 kcal/kg of ideal body weight (IBW)/day (Mlinsek, 2016) and protein intake of 0.75 g/kg of IBW/day for females and 0.84 g/kg of IBW/day for males (Nolte Fong and Moore, 2018).

#### **Low AGE diet (intervention group)**

The low AGE diet will be the same as the standard diet in terms of calories (i.e. 30-35 kcal/kg/day) and protein (0.75-0.84 g/kg/day). However, it will reduce the dietary AGE content by changing cooking methods in food preparation to avoid exposure to dry heat such as frying, broiling, grilling and roasting, and to favour cooking with lower temperatures and high-water content as in stewing, steaming, boiling and poaching. In addition, the low-AGE group will be instructed to choose foods with low content of AGEs based on a food choice list that will contain examples of foods commonly available in the UK to be chosen as "allowed," "moderate intake," or "occasional." The goal will be to reduce dietary AGE intake to less than 8000 kU/day.

Dietary advice will be provided in person by an investigator with training and previous experience as a dietitian. Adherence to diets will be evaluated by means of a 3-day food diary (2 weekdays and 1 weekend day) every month. Monthly forms and written instructions on how to complete the 3-day food diaries will be sent by post to the participants. We will ask participants to return the completed food diaries in a pre-paid envelope. If needed, supplementary relevant diet information will be obtained by telephone consultation once the food diaries have been recorded and returned to the research dietitian.

There will be a follow-up meeting or discussion by telephone with participants randomised to the intervention group after 2 weeks of starting the study in order to reinforce the adherence and understanding of the intervention.

##### **7.3.1. Method of Implementing the Allocation Sequence**

The system to be used to coordinate randomisation is [www.sealed envelope.com](http://www.sealedenvelope.com)

The Chief Investigator, [name] and [name] [name] will be aware of allocation which will be documented in the CRF (paper).

There is no expectation that randomisation codes will need to be accessed out-of-hours or in an emergency.

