**Secondary outcomes:**

- Participant adherence to dietary intervention (achieving dietary AGE intake <8000 kilounits [kU]/day).
- Slope of SAF values over 6 months.
- Change in SAF values at 6 months.
- Change in weight over 6 months.
- Change in aortic pulse wave velocity (aPWV).
- Change in high-sensitive C reactive protein (hsCRP).
- Change in quality of life.

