## **7. STUDY PROCEDURES**

### **7.1. Recruitment**

#### **7.1.1. Patient Identification**

Identification and enrolment of participants from the existing kidney transplant recipient population at The Royal Derby Hospital will be undertaken by the Chief Investigator [name], a member of the transplant team.

Initial contact will be made during a routine follow-up appointment. The initial details of the study and Screening Participant Information Sheet (PIS) will be provided by the usual care team (which may include the researcher). Participants will then be given ample time during their appointment to ask questions and consider whether they wish to participate with screening. Having obtained consent to screen Chief Investigator [name], a member of the transplant team will measure a SAF level. SAF level results are obtained within 3-5 minutes.

Participants with a SAF that is above the general population mean for age will then be invited to participate in the study. The Participant Information Sheet will be provided for the participants to take home. Participants will then be given ample time to ask questions and consider whether they wish to participate before being re-contacted by the Chief Investigator. If they do wish to participate, a further visit scheduled on the same day as their next routine appointment will be arranged to obtain consent and undertake baseline assessments.

It will be explained to the potential participant that entry into the study is entirely voluntary and that their treatment and care will not be affected by their decision. It will also be explained that they can withdraw at any time. In the event of their withdrawal, it will be explained that their data collected so far cannot be erased and will be used in the final analyses where appropriate.

The participant's general practitioner will not be informed about the study because there are no implications for other aspects of treatment.

Participants will not be paid to participate in the study. Travel expenses will be offered for any hospital visits in excess of usual care. The majority of study assessments will be timed to take place at the time of routine visits, treatment or assessment.

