#### 7.4. Study Assessments

Once eligible participants have read the PIS and given their informed consent, relevant participant characteristics will be extracted either from electronic data captured in medical records and from a self-reported questionnaire at baseline and will include demographic characteristics, educational level, employment status, duration of renal replacement therapy, transplant type and vintage, number of rejection episodes, aetiology of CKD, medical history (e.g. history of cardiovascular disease, diabetes and hypertension), current co-morbidities, alcohol history, smoking status and current medication.

The accumulation of AGEs will be assessed by measuring SAF using a validated Autofluorescence Reader Standard Unit version 2.4.3 (AGE Reader, DiagnOptics, Groningen, The Netherlands) at baseline, 3 and 6 months, as described in more detail elsewhere (Shardlow et al., 2020). In brief, the AGE Reader directs an ultraviolet excitation light (intensity 300-420 nm) through an illumination window of approximately 1 cm^2 on a skin area (free of visible vessels, scars, tattoos or any other skin irregularities) of the volar surface of the forearm at approximately 10 cm below the elbow. The AGE Reader then measures the amount of emitted light that is reflected back from the skin (intensity 300-600 nm) using a spectrometer (AVS-USB2000, Avantes Inc., Eerbeek, The Netherlands) and a 200-µm glass fibre. SAF is calculated by dividing the average emitted light intensity in the range between 420-600 nm by the average excitation light intensity in the range between 300-420 nm and expressed as arbitrary units (AU). Three measurements will be obtained and the average of these will be used for analysis. Valid SAF readings cannot be obtained when the skin reflectivity is lower than 6% (Mulder et al., 2006); therefore, persons with dark skin colour (i.e. Fitzpatrick skin colour type V-VI), who have an ultraviolet reflectance of less than 6%, will be excluded from this study.

Routine blood/laboratory tests will be performed at baseline, 3 and 6 months and will include haemoglobin, white cell count, hsCRP, glucose, HbA1C, urea, creatinine, potassium, phosphate, calcium, sodium, albumin, total proteins, cholesterol, triglycerides, intact parathyroid hormone and immunosuppression levels.

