## 7.5. Schedule of Assessments

Study Procedures/Assessments	Screening	Recruitment	Baseline	Months						Post-intervention
				1	2	3	4	5	6	
Eligibility assessment	x									
Study discussed and PIS given		x								
Informed consent		x								
Randomisation		x								
Participant characteristics			x							
Skin autofluorescence	x		x		x				x	
Routine blood tests			x		x				x	
3-day food diaries			x	x	x	x	x	x	x	
Dietary AGE food frequency questionnaire			x		x				x	
Subjective Global Assessment			x		x				x	
Handgrip strength			x		x				x	
Anthropometric measurements			x		x				x	
Cardiovascular evaluation			x		x				x	
Quality of life questionnaire (EQ-5D-5L)			x		x				x	
Treatment adherence				x	x	x	x	x	x	
Qualitative study interviews										x
Adverse event assessments				x	x	x	x	x	x	
Physician's Withdrawal Checklist				x	x	x	x	x	x	

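### The schedule lists randomisation ahead of baseline, no section says baseline is completed first, and the reader of SAF and aPWV after screening is not stated

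*Combined protocol and SAP*

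**What the plan says.** - **Section 7.5, Schedule of Assessments.** The row "Randomisation" has its single mark under Recruitment, beside the information sheet and consent rows. The next column, Baseline, holds SAF, bloods, the food diary, the AGE food frequency questionnaire, SGA, handgrip, anthropometry, the cardiovascular evaluation (which includes aPWV) and EQ-5D-5L.
- **Section 7.1.1, Patient Identification.** For those who wish to join, "a further visit scheduled on the same day as their next routine appointment will be arranged to obtain consent and undertake baseline assessments". Randomisation is not placed within that visit. At the earlier screening contact, "Having obtained consent to screen Chief Investigator [name], a member of the transplant team will measure a SAF level".
- **Section 7.3.1.** The Chief Investigator and other named staff "will be aware of allocation which will be documented in the CRF (paper"). Section 9.1 makes the same paper CRF the data collection tool.
- **Section 7.4, Study Assessments.** For baseline, 3 and 6 months, "The accumulation of AGEs will be assessed by measuring SAF using a validated Autofluorescence Reader Standard Unit version 2.4.3"; no operator is named. On the reading itself, "Three measurements will be obtained and the average of these will be used for analysis". No operator is named for aPWV either, and no section provides for a masked assessor.
- **Section 3.2.** The primary outcome is SAF at 6 months. Seven secondary outcomes follow, among them "Change in quality of life".
- **Sections 10.3.2 and 10.5.** Groups are compared at 6 months by t-test or Mann-Whitney test, with no adjusted analyses.

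**The concern.** Baseline measurements are comparable between arms because they are taken before anyone can react to the allocation. Here participants cannot be masked: one arm is told to change how it cooks and what it chooses. Someone who already knows that may describe their usual diet or rate their health differently on a form labelled baseline. A member of staff who knows the arm may, to a smaller degree, handle an SAF or aPWV reading differently. A later adjustment for baseline would not repair this, because the covariate itself would have been measured after allocation.

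The stake goes beyond this study's own comparisons. Section 3.1 lists effect estimates for sizing a larger trial, and the choice of that trial's primary outcome, among its objectives. A distorted change score would pass into both.

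**Working it through.** **1. Is there a stated order?** Three places bear on it.

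| Place | What it fixes | What it leaves open |
|---|---|---|
| 7.5 | Randomisation in Recruitment; baseline measures in the next column | Whether columns are strict time points |
| 7.1.1 | Consent and baseline at one visit | Where randomisation falls in that visit |
| 7.3 and 7.3.1 | Method, randomisation system, who knows the arm | When the allocation is requested |

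The only order on paper is randomisation, then baseline. Nothing reverses it.

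**2. Which outcomes would a contaminated baseline reach?** Let the recorded baseline differ from its unaware value by d1 on average in the low-AGE arm and d0 in the control arm.

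- Difference in change = (low-AGE 6-month minus baseline) minus (control 6-month minus baseline). Its error is -(d1 - d0): one for one, whatever the number of participants.
- SAF slope: the calculation method is not stated. Assuming least squares on months 0, 3 and 6, the centred times are -3, 0 and 3, so slope = (3 x month 6 - 3 x month 0)/18 = (month 6 - month 0)/6. The error is -(d1 - d0)/6 per month.
- Primary outcome: the 6-month difference contains no baseline term, so its error from this source is 0.

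Of the seven secondary outcomes, six use a baseline value. Sorted by how knowledge of the arm could act:

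- Direct route (self-report): quality of life, 1.
- Limited route (instrument reading taken by staff): SAF change, SAF slope, aPWV change, 3.
- Little route (laboratory assay or weight): hsCRP, weight, 2.
- Total 1 + 3 + 2 = 6. The seventh, adherence, is defined by intake under 8000 kU/day and uses no baseline value.

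The baseline AGE questionnaire and diary are also self-reports and are exposed as descriptive baseline data. The documents give no basis for a value of d1 - d0, so no size can be attached to the bias.

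**3. Follow-up readings.** First, the plan's own figure (section 10.1: SD 0.64, difference 0.6, 80% power, alpha 0.05, taken as two-sided):

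- n = 2 x (1.960 + 0.842)^2 x 0.64^2 / 0.6^2 = 17.9, so 18 per group, as stated.
- Power at 18 by the normal approximation is 80.3%; 36/0.9 = 40 in total. Both agree with the plan.

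Next, an illustration only. Suppose there is no true effect, but follow-up reading is unmasked and shifts the arms apart by a systematic b AU. With SE = 0.64 x sqrt(2/18) = 0.213, the two-sided false-positive rate is Phi(-1.96 - b/SE) + 1 - Phi(1.96 - b/SE).

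| Assumed b (AU) | False-positive rate |
|---|---|
| 0.05 | 5.6% |
| 0.10 | 7.6% |
| 0.20 | 15.5% |
| 0.30 | 29.0% |

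These values of b are assumptions. They show what unmasked reading could do to the primary outcome if it happened and if the shift were systematic across an arm.

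**The case against.** **The schedule columns are weak evidence of sequence.** Recruitment is not one moment: it includes giving out the information sheet, which 7.1.1 places before the consent visit. In the text copy, the mid-study marks also sit under month 2 where 7.4 says month 3, so cell positions need care. This stands in part. However, the early columns agree with the text (SAF at screening and again at baseline, none at recruitment), and no other statement puts baseline first. The true order may be sound; the protocol does not secure it.

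**A reader might infer that the Chief Investigator takes every SAF reading and so knows the arm at each.** The documents do not support that. They name that person as operator only at screening, before allocation, and are silent on who reads SAF and aPWV afterwards.

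**A reader might infer that the operator chooses the site and repeats readings freely.** Section 7.4 places the reading on the volar forearm about 10 cm below the elbow, averages three, and refers to a published description for further detail. Discretion is limited. What 7.4 does not state is which arm is used, whether the site is the same at each visit, and when a repeat is allowed.

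**This is a 40-person feasibility study of a diet that cannot be masked.** That is true, and it excuses open delivery. It does not justify measuring baseline after allocation, which costs little to avoid.

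**Conclusion.** The concern holds as a sequencing fault with a silence beside it. The sequence the protocol gives allows allocation to be known before baseline is measured. The outcome most directly exposed is change in quality of life, together with the baseline dietary AGE and diary data; SAF change, SAF slope and aPWV change are exposed to a lesser extent. It would be wrong to say that every change outcome is biased, since hsCRP and weight have little route to bias, or that the order affects the primary outcome, which is an unadjusted 6-month value.

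Unmasked follow-up reading of SAF and aPWV is a plausible inference, because the only named SAF operator knows the allocation. It is not a documented fact. The conclusion rests on reading the schedule as the intended order; the size of any bias cannot be derived from the documents.

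**What to change.** 1. **Section 7.5:** move Randomisation to after Baseline.
2. **Sections 7.1.1 and 7.3:** state that the allocation is requested only once all visit-based baseline measurements and questionnaires are complete.
3. **Baseline 3-day diary (7.4):** it covers two weekdays and a weekend day, so it cannot be finished within the visit. Either send it out beforehand, with consent arranged so that section 7.2 is respected, or say explicitly that it is collected after allocation and is not an unbiased baseline.
4. **Section 7.4, minor addition:** same arm and site at each visit, first three valid readings kept, repeats only on a device error, all three values recorded. State who takes SAF and aPWV after screening. If no masked assessor is used, report outcome assessment as open. Masking only when a suitable colleague happens to be on duty would mix masked and unmasked readings and is best avoided.

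**Cost.** Items 1, 2 and 4 are table and wording changes. Allocation and dietary advice come slightly later. Item 3 needs some logistics, because the diary must have its own timing and consent may have to be taken earlier. Sample size is unaffected.

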#### 7.4. Study Assessments

Once eligible participants have read the PIS and given their informed consent, relevant participant characteristics will be extracted either from electronic data captured in medical records and from a self-reported questionnaire at baseline and will include demographic characteristics, educational level, employment status, duration of renal replacement therapy, transplant type and vintage, number of rejection episodes, aetiology of CKD, medical history (e.g. history of cardiovascular disease, diabetes and hypertension), current co-morbidities, alcohol history, smoking status and current medication.

The accumulation of AGEs will be assessed by measuring SAF using a validated Autofluorescence Reader Standard Unit version 2.4.3 (AGE Reader, DiagnOptics, Groningen, The Netherlands) at baseline, 3 and 6 months, as described in more detail elsewhere (Shardlow et al., 2020). In brief, the AGE Reader directs an ultraviolet excitation light (intensity 300-420 nm) through an illumination window of approximately 1 cm^2 on a skin area (free of visible vessels, scars, tattoos or any other skin irregularities) of the volar surface of the forearm at approximately 10 cm below the elbow. The AGE Reader then measures the amount of emitted light that is reflected back from the skin (intensity 300-600 nm) using a spectrometer (AVS-USB2000, Avantes Inc., Eerbeek, The Netherlands) and a 200-µm glass fibre. SAF is calculated by dividing the average emitted light intensity in the range between 420-600 nm by the average excitation light intensity in the range between 300-420 nm and expressed as arbitrary units (AU). Three measurements will be obtained and the average of these will be used for analysis. Valid SAF readings cannot be obtained when the skin reflectivity is lower than 6% (Mulder et al., 2006); therefore, persons with dark skin colour (i.e. Fitzpatrick skin colour type V-VI), who have an ultraviolet reflectance of less than 6%, will be excluded from this study.

Routine blood/laboratory tests will be performed at baseline, 3 and 6 months and will include haemoglobin, white cell count, hsCRP, glucose, HbA1C, urea, creatinine, potassium, phosphate, calcium, sodium, albumin, total proteins, cholesterol, triglycerides, intact parathyroid hormone and immunosuppression levels.

Nutritional assessments will be performed at baseline and at 3 and 6 months of treatment and will include: 3-day food diary (2 weekdays and 1 weekend day) to assess energy, fat and protein intake; a validated food frequency questionnaire to evaluate dietary AGE intake (Luévano-Contreras et al., 2013); the 7-point scale SGA for the classification of the nutritional status (well-nourished [SGA scores 6-7] or malnourished [SGA scores 1-5]); handgrip strength and anthropometric measurements and indexes, including weight, height, body mass index (BMI), mid-arm circumference, triceps skinfold thickness and mid-arm muscle circumference.

Cardiovascular evaluation will be performed at baseline, 3 and 6 months of treatment and will include traditional cardiovascular risk factors such as blood pressure, HbA1c, BMI and cholesterol. In addition, aPWV (a measure of arterial stiffness) will be assessed using the validated Vicorder device (Skidmore Medical, Bristol, UK) which is a predictor of cardiovascular mortality and morbidity (Lioufas et al., 2019).

Health-related quality of life will be evaluated at baseline, 3 and 6 months of follow-up with the EQ-5D-5L questionnaire.

### **Nested Qualitative Study**

A sample of (n=15) participants will be purposefully selected; n=10 from the intervention group and n=5 from the control group, ensuring as far as possible that the sample includes a diverse representation of the study population for age, gender and ethnicity.

Potential participants will be given or sent an invitation letter and PIS, have the study explained to them and consented separately.

Semi-structured interviews will take place on completion of the intervention period broadly considering the acceptability and tolerability of the intervention in addition to the study process. These interviews will be facilitated by a trained researcher who is not a part of the clinical team to encourage free expression by the individuals involved. The interview will take place at a time and location convenient to the participants and will take about 60 minutes.

Data will be collected via digital audio equipment and transcribed by a Trust vendor qualified transcription service. Analysis will follow the conventions of framework analysis as outlined by Gale et al., 2013. Framework analysis involves a seven-stage process of coding and organising qualitative data in order to provide a structured interpretation of the data, which is finally presented in themes. The stages are: 1. Transcription, 2. Familiarisation with data, 3. Coding, 4. Developing a working analytical framework, 5. Applying the analytical framework, 6. Charting the data into the framework matrix, 7. Interpreting the data. The initial coding and development of the analytical framework will be in order to consensually develop the framework.

## 7.5. Schedule of Assessments

Study Procedures/Assessments	Screening	Recruitment	Baseline	Months						Post-intervention
				1	2	3	4	5	6	
Eligibility assessment	x									
Study discussed and PIS given		x								
Informed consent		x								
Randomisation		x								
Participant characteristics			x							
Skin autofluorescence	x		x		x				x	
Routine blood tests			x		x				x	
3-day food diaries			x	x	x	x	x	x	x	
Dietary AGE food frequency questionnaire			x		x				x	
Subjective Global Assessment			x		x				x	
Handgrip strength			x		x				x	
Anthropometric measurements			x		x				x	
Cardiovascular evaluation			x		x				x	
Quality of life questionnaire (EQ-5D-5L)			x		x				x	
Treatment adherence				x	x	x	x	x	x	
Qualitative study interviews										x
Adverse event assessments				x	x	x	x	x	x	
Physician's Withdrawal Checklist				x	x	x	x	x	x	

## 7.6. Withdrawal Criteria

Participants will be withdrawn from the study if they withdraw their consent at any point or decline to comply with the dietetic intervention or develop malnutrition. Female participants will be withdrawn from the study if they become pregnant.

Participants may be withdrawn from the study either at their own request or at the discretion of the Investigator. The participants will be made aware that this will not affect their future care. Participants will be made aware (via the information sheet and consent form) that should they withdraw the data collected to date cannot be erased and will be used in the final analysis.

If participants fail to attend for their study visits, a member of the research team will try to contact them by telephone within 24 hours of their appointment and by written correspondence within a week of the missed appointment. Multiple attempts at contact will be made by the research team over a period of a month before stating that a participant has been lost to follow-up.

Data that is collected prior to withdrawal will be kept and analysed as part of the data set. The date, time and reason for participant withdrawal will be documented on the case report form (CRF).

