### **3.2. Outcome**

**Primary outcome:** SAF values at 6 months.

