### **10.1. Sample Size Calculation**

As this is a feasibility RCT, no formal sample size calculation is required; however, the aim will be to recruit 40 kidney transplant recipients to test the study procedures and the feasibility of delivering the intervention. Power calculation using ClinCalc indicates that, assuming an SAF value of  $2.81 \pm 0.64$  AU in the control group (Crowley et al., 2013), having a sample size of 18 in each group would give 80% power ( $\alpha=0.05$ ) to detect a difference in SAF of 0.6 AU between the groups at 6 months. The proposed recruitment would achieve this and allow for 10% drop-out.

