#### **10.3.2. Outcome Analysis**

Summary measures of all baseline variables will be calculated and reported. Primary and secondary outcomes will be compared between the two groups (Low AGE Diet vs. Standard Diet) at 6 months using a t-test if data are normally distributed or a Mann Whitney U test if not. Analysis will be by intention to treat.

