#### **10.7. Analysis Groups**

The two groups for analysis will be the Low AGE diet and Standard diet groups. Analyses will be by intention to treat and will include all participants who were randomised and received at least one session of dietary counselling regarding their diet (all-treated population).

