## **10.8. Procedure(s) to Account for Missing or Spurious Data**

Missing data will be omitted from the analyses. The group sizes are too small to consider multiple imputations.

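### Section 7.6 withdraws participants who decline the diet, so the 6-month SAF comparison loses people whom the intention-to-treat population is meant to include

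*Combined protocol and SAP*

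**What the plan says.** - **Withdrawal (section 7.6).** Participants will be "withdrawn from the study if they withdraw their consent at any point or decline to comply with the dietetic intervention". This is a firm rule, and it removes the person from the study, not only from the diet. The same section then says "Data that is collected prior to withdrawal will be kept and analysed as part of the data set". It describes no visit or measurement after withdrawal.
- **Primary outcome (section 3.2).** "SAF values at 6 months".
- **Comparison (section 10.3.2).** "Primary and secondary outcomes will be compared between the two groups (Low AGE Diet vs. Standard Diet) at 6 months", by t-test or Mann-Whitney test. Section 10.5 plans no adjusted analysis.
- **Population.** Section 10.3.2 states "Analysis will be by intention to treat". Section 10.7 repeats this and says that the analyses "will include all participants who were randomised and received at least one session of dietary counselling". Neither section sets an adherence condition.
- **Missing data (section 10.8).** "Missing data will be omitted from the analyses". Multiple imputation is ruled out because the groups are small.
- **Use of the result (section 3.1).** The effect estimate is to inform the sample size of a larger trial. Fidelity and adherence are also objectives.

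**The concern.** Someone who has one counselling session, then declines the diet and is withdrawn before month 6, belongs to the section 10.7 population but has no primary outcome value. The comparison is then made among those who did not decline, under an intention-to-treat label. A 6-month SAF that was never measured cannot be recovered at analysis.

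Two ambiguities make the extent hard to judge. The trigger is undefined: it could mean open refusal only, or something wider. The arm is also unclear. Section 7.3 uses the term intervention group for the low-AGE arm, which would make the loss one-sided, but it also provides dietary advice to both arms, which would allow withdrawals in either.

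The estimate carried forward to size a larger trial is at stake. So is the adherence outcome, because section 10.8 leaves it unclear whether withdrawn participants stay in the denominator.

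**Working it through.** **The plan's own figure.** Section 10.1 gives a difference of 0.6 AU, SD 0.64, α = 0.05 and 80% power. Per group, n = 2(1.960 + 0.842)² × 0.64² / 0.6² = 17.86, so 18, with normal-approximation power of 80.3%. Then 36/0.9 = 40. The stated figures reproduce with a two-sided α. At 1:1 allocation there are 20 per arm, and the 10% allowance is 4 people.

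**How the value is lost.** Section 7.6 ends participation, section 10.3.2 tests 6-month values only, and section 10.8 drops missing ones. Retained baseline data, and a 3-month SAF if already taken, may serve the slope outcome. They do not enter the 6-month test.

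**Size of the bias.** The documents give no rate of declining, so the following inputs are assumptions.

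- The effect, as a reduction in SAF, is 0.6 AU in those who stay. The control diet has no effect.
- qL and qC are the shares declining in the low-AGE and control arms.
- r is the share of the 0.6 AU that decliners receive.
- gL and gC are decliners' minus stayers' untreated SAF in each arm, ranged from -0.3 to +0.3 AU.

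Formulas:

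- Effect in all randomised = 0.6[(1 - qL) + r·qL]
- The plan's estimate = 0.6 + qL·gL - qC·gC
- Overstatement = 0.6·qL(1 - r) + qL·gL - qC·gC

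One low-AGE decliner (qL = 1/20 = 0.05), with g = 0, gives 0.6 × 0.05 = 0.03 AU at r = 0 and 0.015 AU at r = 0.5. The remaining rows suppose that all 4 allowed drop-outs are decliners.

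| Decliners, low-AGE v control | r | Effect in all randomised (AU) | Overstatement, g = 0 (AU) | Overstatement, g from -0.3 to +0.3 (AU) |
|---|---|---|---|---|
| 2 v 2 | 0 | 0.54 | 0.06 | 0.00 to 0.12 |
| 2 v 2 | 0.5 | 0.57 | 0.03 | -0.03 to 0.09 |
| 4 v 0 | 0 | 0.48 | 0.12 | 0.06 to 0.18 |
| 4 v 0 | 0.5 | 0.54 | 0.06 | 0.00 to 0.12 |
| 0 v 4 | any | 0.60 | 0.00 | -0.06 to 0.06 |

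**Against random error.** The 95% half-width is t(0.975, df) × 0.64 × √(1/n1 + 1/n2). It is 0.41 AU at 20 v 20, 0.43 at 18 v 18 and 0.44 at 16 v 20.

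**Consequence for a larger trial sized on 0.60 AU.** The same sample size formula gives 19.79 per arm at 0.57 AU, 22.05 at 0.54 and 27.91 at 0.48, against 17.86. The shortfall is 1 - (effect/0.60)², which is 10%, 19% and 36%. If a 10% drop-out inflation (17.86/0.9 = 19.85) becomes usable sample, the shortfall is about 0%, 10% and 29%.

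**The case against.** The strongest reply is that the trigger is narrow. Section 7.6 speaks of declining, not of failing to reach the target. Adherence is checked monthly by food diary, intake below 8000 kU/day is a secondary outcome, and adherence is an objective. Such a design expects people who miss the target to stay in. On that reading only active refusers are lost, and some of them would refuse visits anyway. This is the more natural reading and it reduces the likely number. It does not restore the 6-month value of a refuser who would still have attended, and the protocol does not confirm it.

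Second, the four-decliner scenarios are extreme. Section 10.1 says "The proposed recruitment would achieve this and allow for 10% drop-out", which is a general allowance. Using all of it for refusal leaves nothing for other losses, and the 36% shortfall also needs all four in the low-AGE arm with no effect. This stands: those rows are outer cases, and the per-decliner figure is the safer guide.

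Third, sampling error dominates. An interval of 0.60 ± 0.43 runs from 0.17 to 1.03 AU, which under the same formula means roughly 6 to over 200 per arm. That also stands, and it limits the severity. The interval does not, however, show the bias.

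Fourth, withdrawal reasons are recorded, and losses are reported by arm (sections 7.6 and 10.3.1). A reader would see the loss but would still lack the value.

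**Conclusion.** The concern holds. Sections 7.6, 10.3.2, 10.7 and 10.8 cannot all operate as written: decliners are counted in the intention-to-treat population and are absent from its primary comparison. That conflict rests on the text alone and is firm.

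The size is conditional. It is 0.015 to 0.03 AU per low-AGE decliner, assuming 0.6 AU in those who stay, half or no effect in decliners, and no selection difference. Overstatement is the expected direction but is not certain. With an assumed selection difference of up to 0.3 AU either way, several scenarios include zero or a reversed bias. Only people withdrawn after a first counselling session and before the 6-month measurement bear on the conflict, because anyone who leaves before counselling is already outside the section 10.7 population. This should be fixed, but in a feasibility study with so wide an interval it does not invalidate the work.

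**What to change.** 1. In section 7.6, separate not following the assigned diet from withdrawal from the study. Invite participants who decline the diet but still consent to attend the remaining scheduled assessments, including 6-month SAF.
2. Define what counts as declining to comply, and state which arm or arms it covers.
3. Reconcile sections 7.6, 10.3.2, 10.7 and 10.8, and analyse participants in the arm assigned whatever their adherence.
4. State the denominator for the adherence outcome. It should match the section 10.7 population in the low-AGE arm, with missing records shown separately.
5. The other withdrawal rules in section 7.6 are for the sponsor to reconcile with the intention-to-treat statement. Report by arm, with reasons, the 6-month outcomes still missing.

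The cost is protocol wording and attendance at visits already scheduled. Section 7.1.1 says an SAF result takes 3-5 minutes and that most assessments coincide with routine visits. The information sheet and consent form may need new wording on withdrawal, and an amendment with ethics review may follow (section 12.10). Some decliners will also refuse visits, so the loss is reduced, not removed. The effect and adherence estimates may look less favourable.
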